3.2. RATIONALE FOR STUDY DESIGN AND MEASURES

We chose a randomized controlled trial, as it is the most rigorous study design and will allow us to directly compare the intervention against usual care. The alternatives, a parallel cohort study or pre-post- study, would not have the same level of rigor, which would undermine study findings. The consequence of this weaker design is that the findings would be less likely to be integrated into practice, thereby wasting the resources and the efforts by the participants. Given the existing literature, we decided that a high quality randomized controlled trial would be appropriate.

The primary outcomes chosen—process, effectiveness, cost effectiveness—allow us to develop the scientific evidence to test this intervention. The robust measures are patterned on Coleman's initial work and can speak to the value proposition for this model. The specific measures are as follows:

Figure 1: Research Framework, Aims, and Processes

Socio-demographic measures (Table 2, Section 1): Standard characteristics will be collected to compare the intervention and control groups and if necessary include these factors as covariates in our analyses. Health system structural factors will also be collected.

ED care & CTI program clinical measures (Table 2, Section 2): We will collect the chief complaint and final diagnosis to evaluate differences between the intervention and control groups and to perform sub-analyses on specific conditions (e.g., injury). We will collect discharge information for our outcomes assessment. Finally, we will measure the elapsed time for the clinical activities (e.g., coaching) to assist with sustainability and dissemination.

Covariates (Table 2, Section 3): Factors that may affect older adults' outcomes and will be collected to include in our analysis. Cognitive status, depression, anxiety, and social isolation are associated with worse outcomes and are critical measures.^{62,63,64,65,66}

Outcomes (Table 2, Section 4): To determine the *fidelity* of the CTI and the *acceptability* of the program to patients and caregivers, we must evaluate the Four Pillars and program satisfaction. This will occur through telephone surveys performed 4 and 30 days after ED discharge. Additionally, as part of the CTI, the coaches measure patients' progress in skill transfer. This information will also be collected.

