Patient subjects randomized to the intervention arm (CTI program) must agree to one paramedic coach home visit and up to 3 follow up phone calls to deliver CTI program clinical care over 30 days. The paramedic coach home visit will ideally occur within 24 hours of ED discharge and take approximately 1 hour. This home visit will be scheduled at a time that is convenient for the subject. During the home visit the paramedic coach will review the subject's medications, educate on red flags and emphasize provider follow-up. The phone calls will reinforce the coaching information. These interactions are organized around the validated and nationally implemented CTI program.

In the event a participating subject is admitted to the hospital directly from the initial ED visit (i.e., the primary team changes its mind based on developing results), then the subject (and caregiver where applicable) will be removed from the study because they no longer meet study eligibility criteria.

Caregiver subjects will be asked to complete an ED survey and one follow up research survey by phone at approximately day 30. The ED survey will take approximately 15 minutes to complete, and the call will take approximately 10 minutes to complete and will assess outcome measures. All questions will be voluntary.

Randomization: Randomization will occur at the site-level and occur after the treatment team has indicated that the patient will be likely discharged home, and the subject or legally authorized representative (LAR) has consented to participate on the study and the baseline survey has been completed. At that point, the subject will be randomized. This will be a stratified randomization, based upon whether or not an informal caregiver provides significant support for the patient.

In the infrequent event that the patient is admitted after consenting for the study and being randomized (but before being discharged and leaving the ED), the patient subject (and caregiver where applicable) will be withdrawn from study as an investigator initiated withdrawal because the subject no longer meets eligibility criteria (i.e hospital admission).

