12.2 PLANNED STATISTICAL ANALYSIS

Through the analytic methods used in Aims 2 and 3, we will assess differences between groups related to process outcome measures (Aim 2) and will assess the effectiveness and cost-effectiveness of the ED-to-home CTI (Aim 3). In Aim 4, we will identify predictors of repeat ED use among intervention group subjects. We will characterize of our study sample using descriptive statistics and corresponding measures of variation. We will assess for differences between groups at baseline despite randomization in key characteristics (e.g., demographics, comorbidities) using t-tests for continuous variables and Chi-square tests for categorical variables, using Fisher's exact test where appropriate. These comparisons will enable the identification of covariates to be controlled in our multivariable analyses. If distributional assumptions associated with a particular statistical procedure are violated, we will use appropriate transformations or non-parametric alternatives. Primary analyses will be performed under the intent-to-treat principle, keeping subjects in the group to which they were originally randomized, regardless of compliance or adherence to study procedures. We will conduct sensitivity analyses among subjects who complete all study procedures to evaluate the effect of the intervention among those who complete all study-related procedures. Hypothesis-driven comparisons will be made to control the family-wise type I error rate at 0.05 (two-sided) for the primary hypothesis.

Caregiver Subject Analysis: Although not an original aim of the study, we have obtained permission from the NIH and will perform a limited analysis of caregiver activation. This was only recently added to

the CTI. To compare the caregiver activation between the control and intervention groups, we will administer the FCAT. The FCAT will be scored as 1-6 points per question, for a score ranging from 10-60. We assume that 30% of participants will have caregivers with them, the average score will be 30, and we will look for a 5 point difference. Our sample size will allow a power of >0.8 for a t-test ($\alpha=0.05$).

Hyp 1A: More program participants will demonstrate understanding of their ED discharge instructions, red flags that indicate a worsening of their condition, and how to respond to the red flags three days after ED discharge.

Hyp 1B: More program participants will implement medication changes made in the ED within three days of ED discharge.

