Hypothesis 2A & 2B: To evaluate difference in subjects' self-care competency, Wallston scores will be compared between intervention and control groups using the Wilcoxon Rank Sum test. Any repeat ED use and the number of ED visits during the 30-day follow up period will be compared between intervention and control groups using the Chi-square test and ANOVA as appropriate. To adjust for potential baseline differences between intervention and control subjects, a multiple logistic regression model will be constructed with repeat ED use as the dependent variable, study intervention group as the primary independent variable, and any covariates that were found to be imbalanced at baseline in our bivariate analyses. Multicollinearity between predictor variables will be assessed using multiple correlations (variance inflation factors). We will use the log likelihood ratio to assess overall model fit. We will also check for overdispersion and use Generalized Estimating Equation (GEE) to provide robust estimates of standard errors. Possible interaction effects between the covariates will be inspected and stratified analyses will be performed if there are significant interaction effects. Standard diagnostic measures for logistic regression such as Pearson residual and deviance residual will be used to check the goodness-of-fit of the regression model assumptions and identify any outliers.

Hypothesis 2C: The proposed economic assessment considers the financial costs and benefits of the CTI. Consistent with standard terminology,⁷³ we define *financial benefits* for this study as the consequences of the CTI that are related to health services cost, expenses, salaries, revenues, and other fiscal issues. It is important to recognize that adoption of the CTI will include both fixed (e.g., implementation) and variable (e.g., dependent on units of care delivered/patients served) costs. Dissemination of the program will require additional resources to cover CTI implementation. Hence, we

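### The repeat-ED analysis (Hypothesis 2B) is not built on the randomisation strata: caregiver support is in no model, and site adjustment has no stated method

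*Combined protocol and SAP*

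**What the plan says.** Section 5.1 sets the design: "Randomization will occur at the site-level", and "This will be a stratified randomization, based upon whether or not an informal caregiver provides significant support for the patient". Individual patients are allocated after consent and the baseline survey.

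Section 12.1 sizes the trial on Hypothesis 2B, using a chi-square test. It adds that clustering by site will need adjustment in most analyses. It gives no method and does not say whether 2B is among them.

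Section 12.2, Hypothesis 2A & 2B, says that any repeat ED use and the number of visits "will be compared between intervention and control groups using the Chi-square test and ANOVA as appropriate". A logistic model follows, with arm and "any covariates that were found to be imbalanced at baseline in our bivariate analyses". The opening of section 12.2 applies the same rule to the baseline tests generally: "These comparisons will enable the identification of covariates to be controlled in our multivariable analyses". On standard errors it says: "We will also check for overdispersion and use Generalized Estimating Equation (GEE) to provide robust estimates of standard errors". No cluster unit is named there, nor for the weighted GEE in the missing-data paragraph.

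Section 3.2 says that the covariates in Table 2, Section 3 "will be collected to include in our analysis", but that list contains neither site nor caregiver support. For the socio-demographic measures it says only "if necessary include these factors as covariates in our analyses".

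**The concern.** An analysis should normally reflect the factors used to restrict the randomisation. Here the two factors the design treats as important reach the 2B model only if a baseline test finds them imbalanced, and stratification exists to prevent that imbalance. The selection rule therefore works against including them.

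Two things follow. First, the chi-square test ignores the balance between arms within strata. It overstates the variance of the treatment difference and gives away a little power. Second, mentioning site clustering in one place and GEE without a unit in two others leaves room for an analyst to cluster standard errors on site. There are only two sites (three EDs), and a sandwich variance with two or three clusters is badly anti-conservative. That risk would affect the adjusted odds ratio and the weighted-GEE estimate, not the chi-square test.

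**Working it through.** **The plan's own figure.** Section 12.1 gives 20% versus 15%, two-sided 5%, 80% power and 860 per group. The pooled formula is n = [1.96·√(2·0.175·0.825) + 0.8416·√(0.16 + 0.1275)]² / 0.05² = (1.0532 + 0.4513)² / 0.0025 = 905.4, so 906. The stated 860 does not reproduce; it gives 77.9% power. The 900 left from 1200 after 25% attrition gives 79.8%. This is a separate matter, but it shows there is no spare power.

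**Inputs that had to be assumed.**
- Event rates by stratum: not in the documents.
- Caregiver share: 30%. Section 12.2 uses this for caregivers present with the patient, so it is a proxy for the support stratum.
- Two equal sites.
- Blocking and block size: not stated.
- Imbalance threshold of P<0.05: not stated.

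**Why the chi-square is conservative.** With arms balanced within strata, the true variance is smaller than the chi-square assumes by the factor r = 1 − Var(p_s)/[p̄(1−p̄)], where p_s is the stratum rate. Its real two-sided error is 2[1 − Φ(1.96/√r)]. Two examples with caregiver effects only:
- Rates 17% and 27%: Var = 0.7·0.3·0.10² = 0.0021; r = 1 − 0.0021/0.16 = 0.987; error 4.85%.
- Rates 12.5% and 37.5%: Var = 0.7·0.3·0.25² = 0.0131; r = 1 − 0.0131/0.16 = 0.918; error 4.1%.

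**Simulation at 860 per arm**, 400,000 trials per scenario. It compares the plain chi-square with a Cochran-Mantel-Haenszel (CMH) test stratified by site and caregiver. Control rates are in the order site 1 without/with caregiver, site 2 without/with caregiver; power is for a 5-point effect.

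| Control rates (%) | Error, chi-square | Error, CMH | Power, chi-square | Power, CMH | Gain (points) |
|---|---|---|---|---|---|
| 20/20/20/20 | 0.050 | 0.050 | 0.780 | 0.780 | 0.0 |
| 17/27/17/27 | 0.049 | 0.050 | 0.782 | 0.787 | 0.5 |
| 15/15/25/25 | 0.048 | 0.050 | 0.783 | 0.788 | 0.5 |
| 12/22/21/30.5 | 0.047 | 0.050 | 0.795 | 0.803 | 0.8 |
| 8/20/24/45 | 0.040 | 0.050 | 0.775 | 0.805 | 3.0 |
| 10/35/15/45 | 0.038 | 0.050 | 0.781 | 0.816 | 3.5 |
| 6/30/20/50 | 0.035 | 0.050 | 0.779 | 0.823 | 4.4 |
| 12.5/37.5/12.5/37.5 | 0.041 | 0.051 | 0.791 | 0.818 | 2.7 |

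The last four rows are the strong sets. A separate run at 900 per arm gave each factor the same odds ratio. At odds ratios of 1, 1.5, 2 and 3, chi-square power was 80.0, 79.9, 80.3 and 81.0%, against 80.0, 80.3, 81.2 and 83.2% for CMH.

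**Would the imbalance screen pick the strata up?** In 20,000 simulated trials of 2400 patients:
- Blocks of 4 or 8 within site by caregiver: site flagged 0 times, caregiver 0 times.
- Blocks of 4 within site only: site 0, caregiver 963 (4.8%).
- Simple randomisation: site 1000, caregiver 998 (5.0% each).

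So even with no blocking, each factor is left out in 95% of trials.

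**Standard errors.** Rejection rates in null trials are for a logistic model with arm, site and caregiver as fixed terms. There were 12,000 trials per scenario, over three sets of strata rates and two assumed splits of patients between the second site's EDs.

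| Standard error | Rejection at nominal 5% |
|---|---|
| Model-based | 4.9–5.2% |
| Patient-level robust | 4.8–5.2% |
| Clustered on 2 sites, uncorrected, normal reference | 39–43% |
| Clustered on 3 EDs, uncorrected, normal reference | 25–30% |

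The two-site result can be checked by hand. With site estimates d₁ and d₂, the uncorrected sandwich variance of their mean is (d₁−d₂)²/8, half the usual (d₁−d₂)²/4. The z statistic is therefore √2 times a t with 1 degree of freedom, and P(|t₁| > 1.96/√2 = 1.386) = 0.398.

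**The case against.** The strongest reply is that little depends on this. The chi-square is valid, its power stays at 0.775–0.795 in every scenario, and a factor balanced by design does not confound. That stands: stratifying is a modest gain, not the repair of an invalid test.

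The larger gains need strong strata effects. The strong sets imply caregiver odds ratios of about 2.6 to 6.7, and nothing in the documents supports values that high. That also stands, so the modest rows are the safer guide.

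The 39–43% figure belongs to an analysis the plan never specifies. With one record per patient, GEE robust errors can naturally be read as patient-level, and those behave well. This is fair, and the risk is conditional. But section 12.1 does speak of clustering by site, so the other reading is open, and one sentence would close it.

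Finally, the promise to adjust most analyses for site probably covers the primary hypothesis. That may be so, but the method is still missing, and the promise does nothing for caregiver support. The screening counts follow almost directly from the assumed blocking and the test's alpha. They illustrate the logic of the rule rather than add evidence.

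**Conclusion.** The concern holds. The 2B analysis does not follow the randomisation, and the covariate rule will usually leave the strata out. The consequence for the main test is small and in the safe direction: error of 4.7–5.0% with no or modest strata effects and 3.5–4.1% with strong ones. The power forgone is 0 to 0.8 points, or 2.7 to 4.4 with strong effects. These sizes rest on assumed stratum rates, equal sites and a 30% caregiver share. In no scenario did stratifying lose power. The inflated error from clustering on site is serious, but it arises only if the unspecified GEE is run that way, and it is confined to the adjusted and weighted-GEE results. The change is worth making because it costs nothing and removes an ambiguity in the primary hypothesis.

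**What to change.** In the Hypothesis 2B text, replace the unstratified comparison with an analysis by the randomisation strata. Either of these would serve, and the plan should name which one is the main test:

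- a Cochran-Mantel-Haenszel test stratified by site and caregiver support; or
- logistic regression with arm, site and caregiver stratum as fixed terms, kept whatever the baseline comparisons show.

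Other covariates can still be added. If the logistic model is chosen, say that its odds ratio is conditional on the strata.

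For all repeat-ED models, including any weighted GEE, state that site is handled by the fixed term or stratum, and that standard errors are model-based or patient-level robust, not clustered on site or ED.

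Cost: two or three sentences under Hypothesis 2B and one in the missing-data paragraph. Both factors must be known at randomisation, so no new data are needed.

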The CTI aims to improve *patient activation*, which is measured as having the skills, knowledge, and motivation to participate as effective members of the care team.⁶⁷ We will use the Wallston Perceived Health Competency Scale.

Upon study exit, we will measure our *primary outcome, health care use* within 30 days of ED discharge, through survey and administrative data from both local health systems and the insurers. We will also measure the costs of health care as well as the CTI program.

We will check the Social Security Death Index for death within 30 days for all subjects.

If a subject *withdraws* during follow-up, we will clarify the level of withdrawal that the subject is requesting—cessation of subject contact or removal from the study. If the subject requests cessation of contact, we will continue to review the subject's medical record to obtain health care use (e.g., ED use) outcomes. If a subject is *admitted to a skilled nursing facility*, which occurs in less than 2% of ED patients discharged home, we will track that outcome and measure those costs, but we will not survey those subjects.

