3.3. RATIONALE FOR INTERVENTION

We will implement and test the CTI for the intervention group because of its demonstrated effectiveness and cost-effectiveness, its applicability to the ED patient discharged home, its efficiency, particularly relating to activities in the ED, and its widespread use. We have chosen to use community-based

paramedics as the coaches for the CTI because these individuals are highly trained, available in all communities, and are highly respected by patients. Thus, paramedics are able to perform these visits in follow up to ED visits rapidly. Given that the CTI program has been tested using lay people, trained paramedics should be able to perform the required duties.

Table 2: Measures

	Measures	Time	Source/Approach
1. Demo -	Patient age, gender, marital status, race, ethnicity, education level, primary language, home ownership, living status, home address	ED	Patient survey
	Patient relationship with PCP	ED	Patient survey
	Insurance plan / number	ED	Epic review
	Primary Care Medical Home certification level	ED	Health systems
2. Clinical	New home services (since ED visit)	Day 30	Patient survey
	ED medications prior to assessment, chief complaint, final diagnosis (ICD-10), discharge medications, and instructions	ED	Epic review
	CTI Coaching & Services Forms* Personal Health Record (PHR) Home Visit/PHR Discussion Checklist Follow-up Phone Calls Checklist Patient Activation Assessment Medication Discrepancy Tool Care Transitions Measure - 3	CTI Coach home visit & coach follow up calls	CTI program records
3. Covariates	Medical history, including Charlson Comorbidity Index	ED	Patient survey
	Healthcare: Medications, home services, ED / hospital use	ED	Patient survey/ Epic review
	Health Status: Short Form-12 ⁶⁸	ED	Patient survey
	Disability Status: ADL ⁶⁹	ED	Patient survey
	Cognition: Short Blessed Test (BOMC)	ED	Patient survey
	Social Isolation: PROMIS Social isolation short form	ED	Patient survey
	Depression: PHQ-9	ED	Patient survey
	Anxiety: GAD-2	ED	Patient survey
Health literacy	ED	Patient survey	
4. Outcomes			
	Family Caregiver Activation in Transitions	ED, Day 30	Caregiver survey
	Understanding of red flags	Day 4	Patient survey
	Medication changes implemented	Day 4	Patient survey
	Follow up with PCP, specialists, urgent care	Day 4, 30	Patient survey / Epic review
	Wallston's Perceived Health Competency Scale (PHCS)	ED, Day, 30	Patient survey, Caregiver survey

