	Healthcare use within 30 days of discharge	Day 30	Patient survey / Epic review
	Death within 30 days of discharge (Social Security Death Index)	Day 30	Death Index
	Patient experiences of continuity	Day 30	Patient survey
	Cost of healthcare and CTI program	Day 30	Health systems, study
Program satisfaction	Day 30	Patient, caregiver survey	

*All forms copyrighted by [name]

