include fixed and variable costs in our analysis while excluding costs associated with the research. We will evaluate the economic impact of CTI from the perspective of health care system/insurers, including both the cost of the CTI and the expected healthcare cost reduction due to altered use of ED, hospital, and office visits. Impact on direct healthcare costs (and hence analysis from the insurer perspective) will be most critical to the adoption and dissemination of this care model since insurance organizations (dominant stakeholders through control of payment), are unlikely to reimburse for CTI care unless they assess it as at cost-neutral or better.

The occurrence of events contributing to healthcare costs (e.g., ED visits) will be ascertained from clinical information systems at both health systems. We will estimate the following CTI expenses for the intervention group: hardware and/or software investments; maintenance costs; direct and indirect costs for training; personnel salary and benefit costs, etc. We will estimate the value of direct healthcare resources saved or expended, including both fixed and variable costs. We will use Medicare reimbursement schedules to assign costs to events because of their national scope, relevance to older populations, and alignment with the true costs of care rather than inflated costs or discounted insurance plan reimbursements. We will calculate total direct costs for each individual by taking the product of the costs per visit (price) and utilization by visit type, and summing across categories of utilization for that individual. We will then estimate unadjusted and adjusted incremental costs. The adjusted cost approach uses multivariable regression models to eliminate the effects of differences in population characteristics across comparison groups, if appropriate. To do so, we will estimate the program's monthly and annual costs using multivariable models and then will calculate the incremental cost of the CTI. All prices will be calculated in 2015 dollars. Using collected data, we will extrapolate the costs of running the program and expected benefits over 12-month period and annually. Finally, we will make economic projections of the program's financial sustainability and scalability. We will conduct a series of sensitivity analyses by modifying local wages, population case-mix and program effectiveness to estimate boundaries to program's sustainability and optimal operational conditions.

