2. During research activities, there will also be a systematic collection of AEs and SAEs. As part of the chart review at UW, we will be collecting death, hospitalizations, ED use, and health care utilization. Furthermore, through patient/caregiver surveys we will be collecting the same

information to particularly identify death, hospitalization, ED use, and health care utilization at non-UW facilities. These AEs and SAEs will be flagged by study staff for review.

3. Independent notification, such as through an unsolicited letter or telephone call, of any events that meet AE or SAE criteria will be flagged by study staff for review.

For each of these events, the staff will record a brief description of the experience, the date of onset, the date of resolution, severity, expected, relationship to study treatment, and outcome of this event. The research team will utilize the NIA approved flow sheets and forms to identify and track potential AEs and SAEs.

Events will be reviewed (within one business day of collection) to determine if they meet criteria for an AE or SAE, as well as whether the AEs/SAEs are UP. Depending on the categorization, the following review will occur (See Figure 1):

Any AE will be reviewed within 5 business days of categorization (as above):

1. The information regarding the subject will be accessed and the NIA tracking form will be completed.
2. The site PI designee (who must be a clinician with relevant expertise) will be notified to determine if the event is unexpected, related to participation in the research, or places participants at a greater risk of physical or psychological harm than was previously known or recognized.
3. If the AE is related but expected, then the PI will report the event to the Independent Safety Officer and the NIA with the monthly reports.
4. or not unexpected, then the PI will report the event to the Independent Safety Officer and the NIA with the monthly reports.
5. If the AE is unexpected, the governing IRB will be notified within 10 business days of categorization.
 - a. The other site investigators will be notified promptly for report to their IRB.
6. The event will be discussed on the weekly study oversight call.

Any SAE will be reviewed within 1 business day of categorization (as above):

1. The information regarding the subject will be accessed and the NIA tracking form will be completed.

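### The cost analysis (Hypothesis 2C) names narrower data sources than the plan uses for 30-day healthcare use; the sections should be reconciled so that 2B and 2C rest on the same visits.

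*Combined protocol and SAP*

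**What the plan says.** Two places give the source of the cost data, and both are confined to the health systems and the study itself.

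- Section 12.2, Hypothesis 2C: "The occurrence of events contributing to healthcare costs (e.g., ED visits) will be ascertained from clinical information systems at both health systems".
- Table 2 (section 3.3), row for the cost of healthcare and of the CTI program: "Health systems, study".

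Other places describe 30-day utilization more widely.

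- Section 3.2 measures health care use, which it calls the primary outcome, "through survey and administrative data from both local health systems and the insurers". The next sentence says that costs will be measured too, without naming a source for them.
- Table 2, row for 30-day healthcare use: "Patient survey / Epic review". The row "Follow up with PCP, specialists, urgent care" has the same source, at days 4 and 30.
- Appendix A, section 1.2, says that the patient and caregiver surveys serve "to particularly identify death, hospitalization, ED use, and health care utilization at non-UW facilities".

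Section 12.2 builds cost as "total direct costs for each individual by taking the product of the costs per visit (price) and utilization by visit type", sums it over visit types and takes prices from Medicare schedules. The viewpoint is that of the health care system and insurers, and the insurer's view is treated as decisive for adoption. Section 12.2 mentions insurer claims only under future analyses.

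**The concern.** An insurer pays for ED, hospital and office care wherever it is delivered. The cost formula needs a visit and its type, not a bill from the facility, so a visit reported in a survey could in principle be priced in the same way as one found in the record. If 12.2 is followed as worded, a visit outside the two systems is not ascertained and adds nothing, and a subject whose only care was elsewhere enters with zero cost.

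Three things are at stake. The 2C total may miss part of what the insurer viewpoint is meant to cover. Any saving could be understated while the expense of running the CTI is counted completely, which matters because the plan treats cost neutrality as the test for reimbursement. And the effectiveness result (2B) and the cost result (2C) would rest on different sets of ED visits, so the two could not be read together cleanly.

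**Working it through.** The documents give no effect size, standard deviation, unit price or power for 2C, so there is no 2C figure to reproduce. The check has two parts.

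**1. Sources side by side**

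| Place | Quantity | Health-system records | Survey | Insurers |
|---|---|---|---|---|
| 12.2, Hypothesis 2C | cost events | yes | not named | not named |
| Table 2, cost row | cost | yes (plus study records) | not named | not named |
| 3.2 | 30-day use | yes | yes | yes |
| Table 2, use row | 30-day use | yes | yes | not named |
| Appendix A, 1.2 | ED use, hospitalization, other use | yes | yes, aimed at other facilities | not named |
| 12.2, future analyses | use and claims | – | – | later work only |

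The plan does not settle which utilization is priced.

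**2. Illustration of size**

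Inputs: 20% repeat ED use in controls and a 5-point reduction, hence 15% under the CTI (section 12.1). The outside share s is an assumption: the fraction of subjects with a repeat ED visit who have none inside the two systems.

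Captured proportion = true proportion × (1 − s).

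*Equal s in both arms:* captured difference = 5.0 × (1 − s).

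| s | Control | CTI | Difference (points) | Ratio |
|---|---|---|---|---|
| 0% | 20.0% | 15.0% | 5.0 | 0.75 |
| 5% | 19.0% | 14.25% | 4.75 | 0.75 |
| 10% | 18.0% | 13.5% | 4.5 | 0.75 |
| 20% | 16.0% | 12.0% | 4.0 | 0.75 |

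*Net cost:* with true saving S and programme expense C, the true net saving is S − C. If the whole saving is under-captured by s, the captured net saving is S(1 − s) − C. For a programme at exact break-even (S = C) this is −sC, so s = 20% makes it appear to lose 20% of its own expense.

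*Unequal s:* captured ratio = true ratio × (1 − s for CTI) / (1 − s for control).

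- Control 20%, CTI 10%: 16.0% v 13.5%, difference 2.5. A true ratio of 0.75 appears as 0.844, and a true null as 0.9/0.8 = 1.125.
- Control 10%, CTI 20%: 18.0% v 12.0%, difference 6.0. The ratio appears as 0.667, and a true null as 0.8/0.9 = 0.889.

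These figures concern ED use, not dollars. They show how the mechanism behaves and do not estimate the bias in 2C.

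**The case against.** The strongest reply is that section 12.2 nowhere says that other sources are excluded. Section 3.2 measures 30-day use by survey and by health-system and insurer data, and then turns directly to cost. Since cost is price times utilization, that wider utilization can be read as what 2C prices. This stands as far as intent goes: a reader might infer that the plan has chosen to price outside care at zero, and the documents do not say so. It does not remove the conflict, because the analysis section and the cost row of Table 2 both name narrower sources.

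Other replies also stand.

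- The survey instrument is not in the documents, so it is not shown that facility, date and visit type are recorded for each outside contact. The Appendix A sentence concerns safety events and is worded from the UW side; non-UW literally includes the partner site.
- Section 4.2 requires a UW- or UR-affiliated PCP and county residence in both arms. This limits outside office care, though not outside ED or hospital care.
- A reader might infer that coaching toward an affiliated PCP makes ED under-capture differ by arm. That mechanism concerns office visits and gives no reason for a different outside share of ED visits.
- Surveys have gaps of their own. Section 12.1 expects about 25% attrition, and section 3.2 says that subjects admitted to a skilled nursing facility are not surveyed. Recall could differ by arm, since coached subjects develop a Personal Health Record. Records continue to cover subjects who only stop contact.
- 2C is not the hypothesis that sized the trial.

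**Conclusion.** The point holds as an inconsistency to be resolved: the sources named for 2C are narrower than those named for the utilization that 2C prices. Followed literally, 12.2 leaves outside ED, hospital and office visits out of a cost total meant to reflect the insurer's side, and separates the visit sets of 2B and 2C.

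The size is unknown, because no outside share is given. With equal loss of an assumed 5% to 20%, the absolute ED difference falls from 5.0 to between 4.75 and 4.0 points and the ratio does not move. If the CTI truly saves money, net cost is then biased against it, because its expense is fully counted. A reader might infer that the bias must understate the benefit. With unequal loss it need not: the same formula gives 2.5 or 6.0 points according to which arm loses more, and the documents do not indicate which, if either, applies.

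**What to change.** In section 12.2, state that 2C prices the same 30-day utilization set as 2B: health-system records, plus survey-reported visits at facilities outside both systems, plus insurer data if obtained for this analysis. Remove duplicates where date and visit type allow, say how conflicts between survey and record are settled, and apply the same Medicare schedule throughout. Bring the cost row of Table 2 into line, and say whether the insurer data named in section 3.2 belong to this analysis or only to the future one.

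Report the records-only total alongside as a sensitivity analysis, with survey response by arm.

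The cost is SAP wording and a merge of data that the trial already plans to collect, provided the survey holds enough visit detail to price. The downside is that capture of outside care then depends on response and recall, either of which may differ by arm. The merge also narrows the gap without closing it. If 25% are not surveyed, the rest report completely and non-response is unrelated to outside use, an outside share of 20% leaves 0.25 × 20% = 5% uncaptured, a difference of 5.0 × 0.95 = 4.75 points instead of 4.0.
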